2. OBJECTIVES

Primary Objective:

- To assess the change from baseline in 24-hr proteinuria with dapagliflozin for six weeks relative to placebo treatment in patients with non-diabetic kidney disease and proteinuria > 500 mg/day on stable ACEi or ARB treatment.

Secondary Objectives

- To assess the effect of dapagliflozin 10 mg/d compared to placebo on Glomerular Filtration Rate (GFR) using iothexol clearance
- To assess the effect of dapagliflozin 10 mg/d compared to placebo on systolic/diastolic blood pressure
- To assess the effect of dapagliflozin 10 mg/d compared to placebo on body weight
- To assess the effect of dapagliflozin 10 mg/d compared to placebo on selected neurohormones/biomarkers:
 - Hormones of the RAAS (plasma and urine)
 - Natriuretic peptides
 - Urinary adenosine
 - Co-peptin
 - Immunoglobulin G (plasma and urine)
- To characterize the safety of dapagliflozin vs. placebo by determining the number of hypoglycemia episodes between groups and serious adverse events.

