3. STUDY DESIGN

A double blind randomized placebo controlled cross-over study will be conducted in subjects with Chronic Kidney Disease aged between 18 and 75 years, proteinuria levels between 500 and 3500 mg/24-hour, and an eGFR ≥ 25 ml/min/1.73m² will be enrolled. Patients with type 1 or type 2 diabetes, polycystic kidney disease, glomerulonephritis with flares (lupus or anti-neutrophil cytoplasmic antibodies (ANCA) associated vasculitis) or ongoing active renal inflammation will be excluded. Since each subject is his/her own control, this design requires fewer patients as compared with a parallel study design. A wash-out period after each treatment period has been included in the design to avoid cross-over effects.

The study will consist of a screening visit, a 4-week (up to a maximum of 16-weeks) run-in phase for those subjects not on stable ACEi/ARB treatment, 2 consecutive 6-week double blind treatment periods separated by 6-week wash-out period. Subjects will be randomly assigned to one of the treatment orders as depicted in figure 1.

Figure 1: Study design

Screening	Run-in 4 weeks	Placebo 6 weeks	Wash-out 6 weeks	Dapa 10 mg 6 weeks	Wash-out 6 weeks
Screening	Run-in 4 weeks	Dapa 10 mg 6 weeks	Wash-out 6 weeks	Placebo 6 weeks	Wash-out 6 weeks

The target population will be invited for screening. Subjects who meet all entry criteria and who are already on a stable dose (no changes in dose or type of drug) of ACEis or ARBs for at least 4 weeks proceed directly to randomization. Subjects who had their ACEi or ARB medication changed during the preceding 4 weeks of the screening visit proceed to a run-in phase during which the type and dose of these drugs are stabilized. Subjects will be randomly assigned to one of the two treatment orders as depicted in figure 1. Each treatment period lasts 6 weeks followed by a 6 week wash-out period to avoid cross-over effects. Subjects will have their study visit in the morning in fasted condition.

Subjects will be instructed to take the study medication once daily, in the morning, except on study days; on those days, the study drug will be taken after or during the patient visit.

Measurements:

- During the double blind treatment period, and wash-out period patients will collect a 24-hour urine collection at each visit for measurement of 24-hour protein, albumin, sodium,

potassium, creatinine, and urea excretion. Twenty-four hour urine collections will be performed at:

- o Screening visit

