- o Run-in, day 1, week 3, and week 6 (last day on treatment) of each treatment period, and six weeks after the second treatment period (after the last wash-out period).
- Office systolic and diastolic blood pressure measurements will be performed at day 1, week 3 and 6 (last day on treatment) of each treatment period, and six weeks after the second treatment period.
- Vital signs (heart rate, blood pressure) and body weight, height
- Blood will be sampled for measurement of laboratory assessment outlined in the Table 1 and analysis will be performed by the local laboratory.
- Additional blood will be sampled at Day 1 and week 6 of each treatment period, and six weeks after the second treatment period for shipment to the UMCG for biomarker measurement including RAAS biomarkers, natriuretic peptides, co-peptin, immunoglobulin G, and urinary adenosine.
- Blood and urine samples will be stored for future exploratory biomarker analyses to study the effect of dapagliflozin in this study population
- At the screening visit Demography and significant medical history as defined below will be assessed and recorded on the Medical History/Kidney Diagnosis section of the eCRF.
 - Kidney diagnosis
 - Condition related to kidney disease (i.e. recurrent electrolyte disturbances, hypovolemia, prior events such as Acute Kidney Injury)
 - Cardiovascular diseases
 - Recurrent/severe urinary tract infections, genital infections, urosepsis
 - Recent hospital admission, and reason for admission (within the last year)
 - Reactions to radio-contrast media

- **Time and Events Table**

Parameter	Screening ^a	Run-in	Treatment Period 1				W/O	Treatment Period 2				W/O
Visits	V0	V1	V2	V3	V4	V5		V6	V7	V8	V9	V10
Week			0	1	3	6		12	13	15	18	24
Informed Consent ^a	x											
Randomization			x									
Significant Medical History & Kidney disease diagnosis	x											
Serum or Urine Pregnancy test			x ^c					x ^{c, g}				
24-hour urine ^b	x ^d	x	x		x	x		x		x	x	x
GFR-iohexol			x			x		x			x	x
Plasma PK sample						x					x	
Vital signs	x	x	x		x	x		x		x	x	
Blood sampling ^e	x	x	x		x	x		x		x	x	x
Additional blood sampling			x			x		x			x	x
'Biomarker samples' ^f												
Physical exam	x		x		x	x		x		x	x	x
Telephone visit				x					x			
Dispense Medication			x					x				
Drug accountability						x					x	
Adverse events	x	x	x	x	x	x		x	x	x	x	x
Review medications	x	x	x		x	x		x		x	x	
DNA collection			x									

a Informed consent is obtained before any study specific procedure is done.

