Potentially eligible subjects who complete the screening visit will enter the run-in period if they are not using an ACEi or ARB, or if they are not using a maximum tolerated dose of an ACEi or ARB. During the run-in period, ACEi or ARB will be started or uptitrated towards the maximum tolerated antihypertensive dose. If a patient does not tolerate the maximum dose of an ACEi or ARB, this should be documented in the eCRF and the patient can proceed to the double blind treatment period if all other entry criteria are met.

Visit 1

Subjects who entered the run-in period will return for the run-in visit 4 weeks after starting an ACEi/ARB or after ACEi/ARB dose adjustments. The subject has to be on a stable dose of an ACEi or ARB for at least 4 weeks before randomisation. More visits may be required to make sure that the subject still meet all entry criteria at the end of the run-in period. The run-in period may take up to a maximum of 16 weeks. If the eGFR remains ≥ 25 ml/min/1.73m² and the proteinuria level remains between 500 mg/24hr and ≤ 3500 mg/24hr at the end of the run-in period, the patient qualifies to proceed to the double blind treatment period.

Double-Blind Treatment Period:

Eligible subjects will enter in the randomized, double-blind, treatment period if their ACEi/ARB and diuretic medication is stable for at least 4 weeks and all entry criteria are met. The

randomization codes generated by University Medical Center Groningen will be programmed into the IBM Clinical Development Merge to randomly assign subjects to a treatment arm. The investigational drug will be dispensed by the principal investigator or delegated based on the randomization number.

Subjects will continue to maintain their stable doses of commercially available ACEI or ARB, and diuretics if applicable, throughout the double blind phase. Patients will be counseled to maintain a stable habitual dietary salt intake

Visit 2

The randomization visit procedures should be completed on a single day. The randomization visit procedures will include GFR measurement by plasma clearance of nonradioactive iohexol after a single intravenous dose. The GFR measurement will last approximately 4 hours for patients. The first dose of blinded study medication should only be administered on Day 1 AFTER ALL randomization visit procedures have been completed. Patient will be treated in random order with dapagliflozin 10 mg QD or matching placebo QD.

Visit 3, 4, and 5

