5.1. Analysis of primary outcome

The log-transformed 24-hour proteinuria values will be analyzed by a mixed-effects general linear regression model with treatment and period as fixed factor and patients (nested in sequence) as a random factor. This type of model, which accounts for repeated observations within individuals (measurement occasion at level one, individuals at level two) will allow us to estimate the treatment effect (estimated by restricted maximum likelihood). We will also explore the period-specific treatment effect adding in the model the interaction between the treatment and period covariates. If the baseline characteristics will be considerably different across the three regions included (Malaysia, North America, Europe) we shall consider to include region as a layer in the multilevel model fitted or as fixed effect covariate. We will also analyse the log-transformed 24-hour albuminuria values (a specific protein using the same model as described above).

The change in secondary outcomes, mGFR, eGFR, body weight and systolic blood pressure will be analyzed by the same model as showed for the proteinuria outcome.

In general, the models employed will be:

$$y_{it} = \beta_{0i} + \beta_1 Treat_{it} + \beta_2 Period_{it} + \beta_3 Interaction + \varepsilon_{it}$$

$$\beta_{0i} = \beta_0 + u_{0i}$$

$$\varepsilon_{it} \sim N(0, \sigma_\varepsilon^2)$$

Where y_{it} is the outcome for the individual i at time point t , β_{0i} is the intercept for individual i comprised of a sample-average fixed effect β_0 and an individual effect u_{0i} and ε_{it} is the residual error.

Complete case analyses, that is analysing records that present the whole set of information (outcome and covariates) for every visit of the patients will be performed. Patterns of missing data (for the outcomes and the covariates) will be reported. If the proportion of missing records is higher than 5% and/or we will suspect of particular missing mechanisms we will impute the missing values by multiple imputation using the full conditional specification.

Further, if there will be baseline measurements that are missing we will use the values measured at the screening visit: we will document the frequency of this imputation.

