5.2. Subgroup and sensitivity analyses

The primary and secondary outcomes will be analyzed in the following subgroups:

1. Age (\geq or $<$ 60 years or median)
2. Gender (Male / Female)
3. Region (Asia, Europe, North Am)
4. Proteinuria (\geq or $<$ 1000 mg/24hr)
5. mGFR (\geq or $<$ 45 ml/min/1.73m² or median)
6. Systolic blood pressure (\geq or $<$ 130 mmHg or median)
7. Body mass index (\geq or $<$ 25 kg/m² or median)
8. Kidney Diagnosis
9. Diuretic use (Yes/No)

We will flag patients who have started or changed the dose of any medication that may influence the primary outcome (e.g. NSAID, corticosteroids, diuretic treatment, mineralocorticoid receptor antagonists, and Vitamin D during the double blind treatment periods and perform a sensitivity analysis on the primary outcome excluding them.

Another sensitivity analysis will be performed on the primary outcome where we will use the average of the screening and randomization 24-hr proteinuria value.

All the analyses described in the SAP are based on the intention to treat principle (that is, patients analysed according to the group they were originally assigned). We will also perform the analyses on the primary outcome(s) considering “on treatment” patients defined as those with adherence to study medication \geq 80% (as determined by pill count).

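### The co-medication sensitivity analysis in SAP 5.2 does not flag drug changes made in the wash-out between periods that are still in effect in period 2

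*SAP*

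**What the plan says.** SAP 5.2 states: "We will flag patients who have started or changed the dose of any medication that may influence the primary outcome". A bracketed list of examples follows, and the sentence ends "mineralocorticoid receptor antagonists, and Vitamin D during the double blind treatment periods and perform a sensitivity analysis on the primary outcome excluding them". The bracket is never closed; I read the time window as applying to the whole list.

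The wash-out lies outside that window. Protocol section 3 (and SAP 3.1 in the same words) describes "2 consecutive 6-week double blind treatment periods separated by 6-week wash-out period". The same protocol section lists the two phases side by side when it schedules urine collections: "During the double blind treatment period, and wash-out period patients will collect a 24-hour urine collection at each visit". Its account of Visits 6 to 9 has the second double-blind period starting only after the wash-out.

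On the response variable, SAP 5.1 says: "The log-transformed 24-hour proteinuria values will be analyzed by a mixed-effects general linear regression model with treatment and period as fixed factor". The primary objective in Protocol section 2 is worded differently: "To assess the change from baseline in 24-hr proteinuria with dapagliflozin for six weeks relative to placebo treatment". SAP Table 6 shows change from baseline by period, and SAP Table 2 tabulates baseline characteristics by period.

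On background therapy, Protocol section 3 says: "Subjects will continue to maintain their stable doses of commercially available ACEI or ARB, and diuretics if applicable, throughout the double blind phase". The Time and Events Table marks "Review medications" at Visit 6 (week 12).

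**The concern.** The trial compares each patient's result at week 6 with the result at week 18. A drug that alters proteinuria and is present at only one of those two points mixes its own effect with the treatment effect. The sensitivity analysis is there to show whether such changes drive the result, so its flag should cover the whole interval between the two measurements. As worded, it leaves out the six weeks in the middle.

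A patient whose therapy changed at week 9 and stayed changed would therefore remain in the analysis. Agreement between the primary and sensitivity results would then say less about co-medication than it appears to.

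**Working it through.** **The plan's own figure.** The documents give no figure for this sensitivity analysis, so the sample size sets the scale. Protocol 3.4 uses a paired t-test with two-sided alpha 0.05, a difference of 0.288 on the log scale and an SD of 0.7. Taking 0.7 as the SD of the within-patient difference, 80% power needs 49 completers, and 50 give 81.4%. With 5% dropout, 50/0.95 = 52.6, so 53 are enrolled. The plan's 50 and 53 are reproduced. The standard error with 50 completers is 0.7/√50 = 0.099.

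**Weight of one patient's change.** Assume 25 completers per sequence and complete pairs. For end-of-period values, a patient's contrast D is week 6 minus week 18 in the dapagliflozin-first sequence, and week 18 minus week 6 in the other. The treatment estimate is ½ × (mean D in sequence 1 + mean D in sequence 2). A drug effect s (log scale) present at only one of the two weeks moves D by s, and so moves the estimate by s/(2 × 25) = s/50. The table gives the weight as a multiple of s/50, ignoring sign.

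| Timing of the change | Flagged now? | Weeks 6 and 18 values | Change from own period's baseline (week 0 or 12) |
|---|---|---|---|
| Wash-out, settled by week 12, persists | No | 1 | 0 |
| Wash-out, takes effect only after week 12 | No | 1 | 1 |
| Period 1, in effect by week 6, persists | Yes | 0 | 1 |
| Period 2, in effect by week 18 | Yes | 1 | 1 |
| Short course, effect gone by week 12 | No | 0 | 0 |

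Change from a single week 0 baseline gives the same weights as the week 6 and 18 values, because the common baseline drops out of D.

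**Size of the bias.** The documents give neither the frequency nor the effect of such changes. I assume that a change lowers proteinuria by a proportion r of 20% to 40%, so s = ln(1−r) and the affected patient's contrast moves by 0.22 to 0.51. With k1 affected patients in the dapagliflozin-first sequence and k2 in the other, the shift in the estimate is s × (k2 − k1)/50. With all k patients in one sequence its size is (k/25) × [−ln(1−r)]/2:

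- k = 2, r = 0.20: 0.08 × 0.223/2 = 0.009, and 0.009/0.288 = 3%
- k = 3, r = 0.30: 0.12 × 0.357/2 = 0.021, and 0.021/0.288 = 7%
- k = 5, r = 0.40: 0.20 × 0.511/2 = 0.051, and 0.051/0.288 = 18%

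The largest is 0.051/0.099, about half a standard error. With equal numbers in the two sequences (3 and 3, say) the shift is zero, because the period term absorbs it.

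**As noise alone.** If a fraction f of patients is affected, the SD becomes √(0.7² + f(1−f)s²). For f of 5% to 20% and r of 20% to 30%, it rises to at most 0.714, and power at 50 completers is 79.8% to 81.2%, against 81.4%.

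**The case against.** **The response variable is not settled.** The objective and SAP Tables 2 and 6 can be read as change from each period's own baseline. A wash-out change settled by week 12 then cancels and a persistent period 1 change does not, so the present window picks largely the right patients. This stands, and it makes the full-weight statement conditional. It does not rescue the window entirely: a wash-out change that takes effect only after week 12 has weight 1 on either reading.

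**Such changes should be uncommon.** Protocol 4.2 bars aldosterone antagonists, systemic corticosteroids, immunosuppressants and continuous NSAID use for the whole study, and strongly discourages diuretic and vitamin D adjustments throughout. This also stands, but discouraged changes can still happen, and the sensitivity analysis exists for departures of this kind. Protocol 9.3 plans a rescue-medication covariate covering the whole study, but does not define rescue medication, and the SAP does not repeat that analysis.

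**Imbalance between sequences is not expected in a randomised, blinded trial.** The documents give no evidence of it. It cannot be excluded: the first wash-out follows active drug in one sequence only, and the protocol expects effects on blood pressure and volume. That is inference, with no figure behind it.

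**Stronger readings that a reader might infer.**

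- That wash-out changes are uniquely damaging. They are not; a period 2 change has the same weight and is flagged.
- That ACEi/ARB changes escape the flag because the list does not name them. The sentence covers any medication that may influence the primary outcome, and the named drugs are examples.
- That the blank medication-review cell at Visit 10 leaves changes in the second wash-out unrecorded. Vital signs is blank there too, although the protocol text requires blood pressure at that visit. Weeks 18 to 24 are in any case outside the contrast tested here.

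**Conclusion.** The gap in the wording is real, and its consequence is conditional and modest. As written, SAP 5.2 does not flag a change made in weeks 6 to 12 and still in effect in period 2. Such a change carries full weight if SAP 5.1 analyses end-of-period values or change from a single week 0 baseline, and none if the response is change from a week 12 baseline and the change has settled by then.

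The 3% to 18% range rests on assumed effects of 20% to 40%, on two to five affected patients, and on all of them being in one sequence. Balanced changes add only a little noise. A reader might infer that the primary result is biased by this rule. It is not: the rule governs one sensitivity analysis, and the primary estimate and sample size are the same whichever window is used. What is weakened is the reassurance that this analysis can give.

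**What to change.** In SAP 5.2, replace the present window. Flag any start, stop or dose change of a medication that may influence proteinuria from Visit 2 (week 0) to Visit 9 (week 18), including a change made in the wash-out between periods that is still in effect at Visit 6 (week 12) or later. Use the Visit 6 medication review to identify these. A short course completed within the wash-out need not be flagged, so a patient is not lost for a brief course that bears on neither week 6 nor week 18.

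This window can be used whichever response definition SAP 5.1 is taken to mean, because it includes the wash-out changes that can reach the contrast. The cost is a wording change, a few more exclusions, and a slightly wider interval in this one sensitivity analysis. No new data collection is needed.

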5.3. Supplementary analyses

We will assess the change in primary and secondary outcomes during the dapagliflozin treatment periods with the change in proteinuria/albuminuria after stopping dapagliflozin;

This will be assessed by a longitudinal model as described above assessing the appropriate contrasts.

We will also assess the effect of dapagliflozin using 24-hr protein:creatinine ratio (and albumin:creatinine ratio as dependent variables. The model used for the primary outcome analysis will be used for this analysis.

Finally, the proportion of patients who achieve a proteinuria level <500 mg/g during follow-up will be summarized between dapagliflozin and placebo periods. Additionally, the proportion of patients with 30%, 40%, 50% reduction in proteinuria during follow-up will also be summarized between dapagliflozin and placebo group. McNemar and/or Mainland-Gart tests will be conducted depending on the nature of proportions and on the importance of the sequence order

Adherence on treatment, defined as pill count at least 80% during follow-up, will be summarized by treatment arm and study visits.

6. Evaluation of safety parameters

Counts and percentage per treatment arm will generally summarize all categorical indicators. A breakdown of SAEs stratified by fatal/non fatal status will be presented.

7. Proposed tables and figures

Table 1: Baseline characteristics for all randomised subjects by treatment group and in overall

Baseline Characteristics	Dapa (N=xxx)	Placebo (N=xxx)	Overall (N=xxx)
Categorical variables: n/N (%)			
XXX	xxx xxx	xxx xxx	xxx xxx
XXX	xxx xxx	xxx xxx	xxx xxx
XXX	xxx xxx	xxx xxx	xxx xxx
XXX	xxx xxx	xxx xxx	xxx xxx
Continuous variables:			
N Mean (SD)	xxx xxx xxx	xxx xxx xxx	xxx xxx xxx
Q1 Q2 Q3	xxx xxx xxx	xxx xxx xxx	xxx xxx xxx
min max	xxx xxx	xxx xxx	xxx xxx

Table 2: Baseline characteristics for all randomised subjects by group and by period

Baseline Characteristics	Group 1 Period 1 (N=xxx)	Group 1 Period 2 (N=xxx)	Group 2 Period 1 (N=xxx)	Group 2 Period 2 (N=xxx)
Categorical variables: n/N (%)				
XXX	XXX XXX	XXX XXX	XXX XXX	XXX XXX
XXX	XXX XXX	XXX XXX	XXX XXX	XXX XXX
XXX	XXX XXX	XXX XXX	XXX XXX	XXX XXX
XXX	XXX XXX	XXX XXX	XXX XXX	XXX XXX
Continuous variables:				
N Mean (SD)	XXX XXX XXX	XXX XXX XXX	XXX XXX XXX	XXX XXX XXX
Q1 Q2 Q3	XXX XXX XXX	XXX XXX XXX	XXX XXX XXX	XXX XXX XXX
min max	XXX XXX	XXX XXX	XXX XXX	XXX XXX

Table 3: Descriptive results of follow-up measurements by visits

Variables during follow-up	Group 1 (N=xxx)	Group 2 (N=xxx)	Overall (N=xxx)
Vital signs, BP, Biomarkers:			
Week0			
N Mean (SD)	XXX XXX XXX	XXX XXX XXX	XXX XXX XXX
Week3 (if applicable)			
N Mean (SD)	XXX XXX XXX	XXX XXX XXX	XXX XXX XXX
Week6			
N Mean (SD)	XXX XXX XXX	XXX XXX XXX	XXX XXX XXX
Week12			
N Mean (SD)	XXX XXX XXX	XXX XXX XXX	XXX XXX XXX
Week15 (if applicable)			
N Mean (SD)	XXX XXX XXX	XXX XXX XXX	XXX XXX XXX
Week18			
N Mean (SD)	XXX XXX XXX	XXX XXX XXX	XXX XXX XXX
Week24			
N Mean (SD)	XXX XXX XXX	XXX XXX XXX	XXX XXX XXX

Table 4: Descriptive results for primary outcome by visits

Variables during follow-up	Group 1 (N=xxx)	Group 2 (N=xxx)	Overall (N=xxx)
Primary outcome:			
Week0			
N Mean (SD)	xxx xxx xxx	xxx xxx xxx	xxx xxx xxx
Week3 (if applicable)			
N Mean (SD)	xxx xxx xxx	xxx xxx xxx	xxx xxx xxx
Week6			
N Mean (SD)	xxx xxx xxx	xxx xxx xxx	xxx xxx xxx
Week12			
N Mean (SD)	xxx xxx xxx	xxx xxx xxx	xxx xxx xxx
Week15 (if applicable)			
N Mean (SD)	xxx xxx xxx	xxx xxx xxx	xxx xxx xxx
Week18			
N Mean (SD)	xxx xxx xxx	xxx xxx xxx	xxx xxx xxx
Week24			
N Mean (SD)	xxx xxx xxx	xxx xxx xxx	xxx xxx xxx

Table 5: Descriptive results for secondary outcomes by visits

Variables during follow-up	Group 1 (N=xxx)	Group 2 (N=xxx)	Overall (N=xxx)
Secondary outcome:			
Week0			
N Mean (SD)	xxx xxx xxx	xxx xxx xxx	xxx xxx xxx
Week3 (if applicable)			
N Mean (SD)	xxx xxx xxx	xxx xxx xxx	xxx xxx xxx
Week6			
N Mean (SD)	xxx xxx xxx	xxx xxx xxx	xxx xxx xxx
Week12			
N Mean (SD)	xxx xxx xxx	xxx xxx xxx	xxx xxx xxx
Week15 (if applicable)			
N Mean (SD)	xxx xxx xxx	xxx xxx xxx	xxx xxx xxx
Week18			
N Mean (SD)	xxx xxx xxx	xxx xxx xxx	xxx xxx xxx
Week24			
N Mean (SD)	xxx xxx xxx	xxx xxx xxx	xxx xxx xxx

Table 6: Treatment effect for primary outcome

Primary outcome	Dapa (N=xxx)	Placebo (N=xxx)	Difference (Dapa – Placebo) (N=xxx)	p-value
Primary outcome:				
Change from baseline in overall				
N Mean (SD)	xxx xxx xxx	xxx xxx xxx	xxx xxx xxx	xxx
Change from baseline in period 1				
N Mean (SD)	xxx xxx xxx	xxx xxx xxx	xxx xxx xxx	xxx
Change from baseline in period 2				
N Mean (SD)	xxx xxx xxx	xxx xxx xxx	xxx xxx xxx	xxx

Table 7: Treatment effect for secondary outcomes

Secondary outcomes	Dapa (N=xxx)	Placebo (N=xxx)	Difference (Dapa – Placebo) (N=xxx)	p-value
Secondary outcomes:				
Change from baseline in overall				
N Mean (SD)	xxx xxx xxx	xxx xxx xxx	xxx xxx xxx	xxx
Change from baseline in period 1				
N Mean (SD)	xxx xxx xxx	xxx xxx xxx	xxx xxx xxx	xxx
Change from baseline in period 2				
N Mean (SD)	xxx xxx xxx	xxx xxx xxx	xxx xxx xxx	xxx

Table 8: Treatment effect for primary outcome by pre-specified subgroups

Primary outcome	Dapa (N=xxx)	Placebo (N=xxx)	Difference (Dapa – Placebo) (N=xxx)	p-value
Change from baseline in overall				
Subgroup1				
Yes	xxx xxx xxx	xxx xxx xxx	xxx xxx xxx	xxx
No	xxx xxx xxx	xxx xxx xxx	xxx xxx xxx	xxx
Subgroup2				
Yes	xxx xxx xxx	xxx xxx xxx	xxx xxx xxx	xxx
No	xxx xxx xxx	xxx xxx xxx	xxx xxx xxx	xxx
Subgroup3				
Yes	xxx xxx xxx	xxx xxx xxx	xxx xxx xxx	xxx
No	xxx xxx xxx	xxx xxx xxx	xxx xxx xxx	xxx
Subgroup4				

Yes	XXX XXX XXX	XXX XXX XXX	XXX XXX XXX	XXX
No	XXX XXX XXX	XXX XXX XXX	XXX XXX XXX	XXX
Subgroup XXX				

Figure 1: Patients flow chart based on CONSORT

Figure 2: Primary outcome over time by treatment groups and periods. (

[figure not shown]

Figure 3: Bar charts with changes from baseline to week 6 for primary/secondary outcomes

Figure 4: Process measurements over time

Similar figure as above, but could add more time points in week 3 and week 15.

Figure 5: Forest plot for subgroup analysis for primary outcome
